7.7.1.8. Immunogenicity analyses after receipt of the ad hoc booster vaccination

Study participants who receive the ad hoc booster vaccination, will be removed from the main immunogenicity analyses as of that point in time^{a,b}. A separate immunogenicity analysis will be conducted on the study participants who received the ad hoc booster vaccination, starting at the time of the ad hoc booster vaccination and showing their immune responses at each subsequent time point, as available. The statistical analysis will be descriptive. It will show study participants according to their original vaccination regimen in tables, listings and figures. In addition, the analyses may also be conducted separately by subgroups of study participants who received a COVID-19 vaccine outside of the study vs study participants who did not receive a COVID-19 vaccine outside of the study. A distinction between mRNA vaccines vs other vaccines may be made, if the numbers are sufficiently high. Otherwise, this information will be included in the listings only.

^a Note that participants may already have been removed from the main immunogenicity analyses due to receipt of an unscheduled vaccine (either a COVID-19 vaccine received outside of the study or after crossing over from placebo to active within the study). Refer to the clinical trial protocol amendment 15, section 9.7 for more information.

^b Note that, unless the sample needs to be excluded from the analysis for reasons noted in the above footnote (or other reasons as noted elsewhere in the SAP, e.g. occurrence of a natural infection, etc.), the blood sample taken at the day of the ad hoc booster vaccination can be included in the main analysis. As such, it could both contribute to the main immunogenicity analyses (e.g. assess the long term immunogenicity profile) as well as to the analyses on the ad hoc booster (as a baseline).

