The following analyses will be conducted at the time of the End of Study analysis or at an interim analysis^a:

The number and percentage of participants with at least one molecularly confirmed SARS-CoV-2 infection will be tabulated by vaccine regimen, for the entire study period only^b.

The analysis will be repeated pooling all active regimens vs. placebo, where data from all cohorts will be pooled. If at least 5 molecularly confirmed SARS-CoV-2 infection are observed, vaccine efficacy (VE) will be calculated with a 90% confidence interval (CI). Otherwise, no VE will be calculated and only the above mentioned descriptive statistical analysis will be conducted. The following paragraphs provide the rationale for only calculating VE when at least 5 events are observed, as well as the formula to calculate VE and its 90% CI.

Assuming a true VE of 70%, 23 events of molecularly confirmed SARS-CoV-2 infections are required to offer 80% power to detect vaccine efficacy exceeding zero ($H_0: VE = 0$) when using a one-sided alpha level of 0.05 (i.e. a 90% CI) and a randomization ratio of 4.65:1 (860 active:185 placebo). Assuming a true VE of 90%, 5 events are required to offer 80% power to detect vaccine efficacy exceeding zero ($H_0: VE = 0$) when using a one-sided alpha level of 0.05 (i.e. a 90% CI) and a randomization ratio of 4.65:1 (860 active:185 placebo).

^a All or some of the described analyses may also be performed prior to the End of Study analysis, but after the Primary analysis. Since no formal hypothesis tests are performed, no alpha spending will be applied.

^b Note that the observation period ends at the time of unblinding or receipt of an unscheduled vaccine, whichever occurs first, cf. section 9.7 of clinical trial protocol amendment 15. This censoring rule applies to all efficacy analyses.

The formula to calculate VE (as a percentage) is:

$$VE = 100 \times \left(1 - \frac{p}{r(1 - p)}\right)$$

Where p = proportion of events occurring among the group of participants vaccinated with Ad26.COV2.S, r = the ratio of the number participants vaccinated with Ad26.COV2.S to the number of participants vaccinated with placebo. 90% asymptotic Wald confidence limits will be calculated.

The number and percentage of participants with at least one molecularly confirmed Influenza infection will be tabulated by vaccine regimen, for the entire study period only.

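### VE is computed from vaccinated headcounts although follow-up is cut off participant by participant; this is unbiased only if follow-up is equal in both groups, which the SAP does not assure

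*SAP*

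**What the plan says.** SAP section 7.7.3 tabulates molecularly confirmed SARS-CoV-2 infections by regimen. It then compares active with placebo: "The analysis will be repeated pooling all active regimens vs. placebo, where data from all cohorts will be pooled". With at least 5 infections, VE is 100 × (1 − p / (r(1 − p))) with 90% Wald limits. The two inputs are "p = proportion of events occurring among the group of participants vaccinated with Ad26.COV2.S" and "r = the ratio of the number participants vaccinated with Ad26.COV2.S to the number of participants vaccinated with placebo".

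Footnote b to the tabulation states that "the observation period ends at the time of unblinding or receipt of an unscheduled vaccine, whichever occurs first", and adds: "This censoring rule applies to all efficacy analyses".

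Footnotes in sections 7.6.7 and 7.7.1.8 explain what an unscheduled vaccine is: "either a COVID-19 vaccine received outside of the study or after crossing over from placebo to active within the study".

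Section 7.7.3 reuses the same VE approach for positive non-S protein ELISA results. The SAP contains no person-time, incidence-rate or time-to-event version of VE.

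**The concern.** The numerator and the denominator follow different rules. Cases count only up to each participant's censoring point, but every vaccinated participant adds one full unit to r whether censored early or late. If one group is followed for less time on average, it yields fewer cases at the same hazard, and the headcount formula reads that shortfall as an effect of the vaccine or its absence.

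One censoring route depends on treatment: crossover from placebo to active is open only to placebo recipients. Vaccination outside the study is open to both groups and need not occur at the same rate or time in each. At stake are the VE estimate and its 90% interval, for confirmed infection and for the non-S ELISA endpoint. The Wald limits reflect the number of cases and would not reveal a difference in follow-up.

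**Working it through.** **Inputs from SAP section 7.7.3.** 860 active and 185 placebo participants, so r = 860/185 = 4.649; one-sided alpha 0.05; 23 cases for 80% power at VE 70%, and 5 cases at VE 90%.

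**Input not in the SAP.** f = mean placebo follow-up ÷ mean active follow-up. A range is assumed.

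**1. The plan's own figures.** Given the total number of cases, the active share is binomial.
- Under VE = 0: p0 = r/(1 + r) = 4.649/5.649 = 0.823.
- Under VE 70%: p1 = 0.3r/(1 + 0.3r) = 1.395/2.395 = 0.582.
- Under VE 90%: p1 = 0.1r/(1 + 0.1r) = 0.465/1.465 = 0.317.
- 23 cases, reject if at most 15 are active: alpha 0.038, power 81.2%.
- 5 cases, reject if at most 2 are active: alpha 0.042, power 81.3%.

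Both stated case numbers reproduce. The calculation uses the headcount ratio and so assumes equal follow-up.

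**2. What the formula estimates.** Write N for numbers vaccinated and x for cases, with subscripts a (active) and p (placebo). Since p/(1 − p) = x_a/x_p, the term p/(r(1 − p)) equals (x_a/N_a)/(x_p/N_p), a ratio of risks.

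**3. Effect of unequal follow-up.** Take a constant placebo hazard λ, rare events and mean follow-up T.
- Expected x_a = λ(1 − VE) N_a T_a, and expected x_p = λ N_p T_p.
- Hence x_a/(r x_p) = (1 − VE) T_a/T_p = (1 − VE)/f.
- Estimated VE = 1 − (1 − VE)/f.

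| f | Placebo follow-up relative to active | True VE 70% is estimated as | True VE 0 is estimated as |
|---|---|---|---|
| 1.00 | equal | 70.0% | 0% |
| 0.90 | 10% shorter | 1 − 0.3/0.9 = 66.7% | −11% |
| 0.80 | 20% shorter | 1 − 0.3/0.8 = 62.5% | −25% |
| 0.70 | 30% shorter | 1 − 0.3/0.7 = 57.1% | −43% |
| 1.25 | 25% longer (active 20% shorter) | 1 − 0.3/1.25 = 76.0% | +20% |

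Replacing r by the person-time ratio r/f returns the true VE in every row.

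**4. Set against sampling error.** Take 13 active and 10 placebo cases.
- Headcount formula: 1 − 1.3/4.649 = 72.0%. With Wald limits on the log scale (the SAP does not name the scale), the standard error is √(1/13 + 1/10) = 0.421 and the 90% CI is about 44% to 86%.
- Person-time formula with f = 0.8: r/f = 5.811 and VE = 1 − 1.3/5.811 = 77.6%. The same factor of 0.8 on the risk ratio moves the CI to about 55% to 89%.
- With 2 active and 3 placebo cases (the 5-case minimum), headcount VE is 86%, with a CI of about 36% to 97%.

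**5. The 23-case benchmark.** If the rule of at most 15 active cases were applied, power at VE 70% would fall from 81.2% to 64.2% at f = 0.8. At f = 1.25 the one-sided error under VE = 0 would rise from 0.038 to 0.095.

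**The case against.** The strongest reply is that the headcount formula is not a mistake. It is a coherent risk ratio: the SAP's note on Amendment 1 calls the quantity a relative risk, and it matches the percentages tabulated just before it. With equal follow-up it is right. This stands, so the formula should not be called invalid in itself.

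A reader might infer that placebo follow-up was in fact shorter and VE therefore biased downward. The SAP does not support that. It shows no follow-up by group. Under footnote b, unblinding also ends observation, whichever event comes first; if it precedes crossover and happens at the same time in both groups, crossover adds no imbalance. The footnote refers to protocol section 9.7 (amendment 15), which is not at hand. Nor does the SAP say that participants who suspect placebo seek vaccination elsewhere; that would be conjecture.

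A reader might also infer that pooling cohorts biases VE. That requires allocation ratios and follow-up (or risk) to vary together across cohorts, and the SAP gives neither by cohort.

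Finally, the efficacy endpoints are exploratory, footnote a says there are no formal tests, and at the expected case counts the intervals are wide. The shifts at VE 70% in step 3 lie inside the limits in step 4, and the figures in step 5 describe a benchmark, not a planned decision. Harm monitoring in section 7.7.2 is a separate rule that does not use this VE. These points lower the severity. They do not remove the mismatch, because more cases narrow the interval without correcting the bias.

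**Conclusion.** The point holds in conditional form. Section 7.7.3 pairs a headcount ratio with participant-level censoring and does not say that the combination relies on equal follow-up. The SAP's own list of unscheduled vaccines includes one route open only to placebo recipients, so equality cannot be taken for granted.

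The size and direction of any bias are unknown. On the assumed range of 10% to 30% shorter placebo follow-up, with a constant hazard and rare events, a true VE of 70% is understated by about 3 to 13 percentage points and a true VE of 0 is estimated as −11% to −43%. Shorter active follow-up gives an upward bias; equal follow-up gives none. The consequence is limited to an exploratory estimate and its 90% interval, so the change is advisable but its importance is modest.

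**What to change.** In section 7.7.3, define r as the active-to-placebo ratio of total person-time at risk. Count each participant from first vaccination to the earliest of first event, unblinding, unscheduled vaccine or last contact. State explicitly that the ad hoc booster counts as an unscheduled vaccine here: sections 7.6.7 and 7.7.1.8 remove its recipients from the main safety and immunogenicity analyses, but footnote b does not name it. Apply the same definition to the non-S ELISA endpoint. Report person-time and incidence rates by group beside the percentages.

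The headcount risk ratio can stay as a supplementary figure, and 4.65:1 can stay as a planning assumption.

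The cost is SAP wording and a little more programming; the dates needed are those already required to apply footnote b. When follow-up is equal the new formula gives the same answer as the present one. Person-time does not correct for informative censoring or for incidence that changes over calendar time, and the text should say so.

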Janssen Research & Development

Statistical Analysis Plan

**A Randomized, Double-blind, Placebo-controlled Phase 1/2a Study to Evaluate the Safety,
Reactogenicity, and Immunogenicity of Ad26COVS1 in Adults Aged 18 to 55 Years
Inclusive and Adults Aged 65 Years and Older**

Protocol VAC31518COV1001; Phase [1/2a]

VAC31518 (JNJ-78436735)

Status: Approved
Date: 8 September 2022
Prepared by: Janssen Vaccines & Prevention B.V.
Document No.: EDMS RIM-102684

Compliance: The study described in this report was performed according to the principles of Good Clinical Practice (GCP).
Confidentiality Statement

The information provided herein contains Company trade secrets, commercial or financial information that the Company customarily holds close and treats as confidential. The information is being provided under the assurance that the recipient will maintain the confidentiality of the information under applicable statutes, regulations, rules, protective orders or otherwise.

CHANGES TO PREVIOUS VERSIONS

Amendment 2 (8 September 2022)

This Statistical Analysis Plan (SAP) amendment relates to amendment 16 of the VAC31518COV1001 clinical trial protocol. In this amendment, the booster vaccination at 24 months after completion of the primary regimen is removed in Cohorts 2a (Target Visit Day 731) and 2b (Target Visit Day 787). This is reflected in section 7.1.2. “Phase Definitions”, and other sections where reference was made to that booster vaccination.

Amendment 1 (16 December 2021)

This Statistical Analysis Plan (SAP) amendment relates to amendment 15 of the VAC31518COV1001 clinical trial protocol, in which a single ad hoc booster vaccination with Ad26.COV2.S at the 5×10^{10} vp dose level is offered to all eligible study participants (as defined in the clinical trial protocol).

The SAP amendment describes the planned safety and immunogenicity analyses that will be conducted on study participants who elect to receive the ad hoc booster dose.

The following changes have also been applied during this SAP update:

- Throughout the SAP: references to “final analysis” have been removed since this analysis was removed from the protocol.
- Section **7.7.3**:
 - o The confidence interval method was changed from Clopper Pearson to Wald, because the Clopper Pearson confidence interval cannot be calculated for a relative risk.

TABLE OF CONTENTS

CHANGES TO PREVIOUS VERSIONS.....	2
TABLE OF CONTENTS	3
LIST OF TABLES	4
VERSION HISTORY.....	5
1. INTRODUCTION.....	6

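### The vaccine-efficacy interval was changed to Wald for a reason that does not hold for the SAP's own formula, and it gives no usable limits when the active group has no cases

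*SAP*

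**What the plan says.** Section 7.7.3 pools all active regimens against placebo across cohorts. If at least 5 molecularly confirmed infections occur, it calculates VE = 100 × (1 − p/(r(1 − p))). Here p is the share of events that fall in the active group and r is the ratio of active to placebo participants. For the interval, "90% asymptotic Wald confidence limits will be calculated". No scale is named (p, relative risk or log relative risk), and nothing is said about zero active cases.

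The Amendment 1 change log explains the move from Clopper-Pearson to Wald: "because the Clopper Pearson confidence interval cannot be calculated for a relative risk".

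The 5-event threshold is justified by power at a one-sided 5% level (a 90% interval) with 860 active and 185 placebo participants: "Assuming a true VE of 90%, 5 events are required to offer 80% power to detect vaccine efficacy exceeding zero". A companion statement reads "Assuming a true VE of 70%, 23 events of molecularly confirmed SARS-CoV-2 infections are required to offer 80% power". Section 7.7.3 allows the same approach for the non-S protein ELISA endpoint.

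**The concern.** The reason given for the change would matter for a ratio of two separately estimated proportions. The SAP's formula conditions on the total number of events and depends on a single binomial proportion, which is the setting Clopper-Pearson was made for.

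The replacement is a large-sample method that comes into use at 5 events. Its weakest case is zero cases in the active group, which is also the most favourable result for the vaccine. The power figures that justify the threshold also appear to belong to the method that was dropped. At stake are a missing or meaningless interval in a plausible outcome, and lower limits that look firmer than the data allow.

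**Working it through.** **Inputs (section 7.7.3).** r = 860/185 = 4.6486; one-sided level 0.05, z = 1.645; VE of 0, 70% and 90%. VE of 95% is added here as an assumption.

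**Share of events in the active group.** Solving the VE formula for p gives p = r(1 − VE)/(1 + r(1 − VE)):
- VE 0: 4.6486/5.6486 = 0.8230
- VE 70%: 0.5824
- VE 90%: 0.3173
- VE 95%: 0.1886

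**The SAP's event counts.** Let X be the number of active cases among n events, binomial with parameters n and p. Reject VE = 0 when X ≤ c, with c the largest value for which P(X ≤ c | 0.8230) ≤ 0.05. This is the same as the upper 90% Clopper-Pearson limit for p lying below 0.8230.
- n = 5: c = 2, error 4.2%, power at VE 90% = 0.1483 + 0.3446 + 0.3204 = 81.3%
- n = 23: c = 15, error 3.8%, power at VE 70% = 81.2%

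These are the smallest n with exact power of at least 80%, so both figures reproduce. Approximate methods give, for VE 90% and 70%: score 4.1 and 18.8 events, Wald on p 5.2 and 26.0, log relative-risk Wald 5.4 and 17.5, Schoenfeld 9 and 30. None yields both 5 and 23.

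**Exact limits for VE.** p/(1 − p) rises with p, so VE falls with p. If pL and pU are the 90% Clopper-Pearson limits for p, the lower VE limit is 100(1 − pU/(r(1 − pU))) and the upper is 100(1 − pL/(r(1 − pL))). For X = 2 of 5, pU = 0.8107, so the lower limit is 100(1 − 0.8107/(4.6486 × 0.1893)) = 7.8%.

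**Log-Wald limits.** RR = X/(r(n − X)) and SE = √(1/X + 1/(n − X)). For X = 2 of 5, RR = 0.1434 and SE = 0.9129, so the lower limit is 100(1 − 0.1434 × e^(1.645 × 0.9129)) = 35.6%.

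At 5 events:

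| Active cases | VE | Exact 90% CI | Log-Wald 90% CI |
|---|---|---|---|
| 0 | 100% | 82.3 to 100 | undefined |
| 1 | 94.6% | 58.7 to 99.8 | 66.2 to 99.1 |
| 2 | 85.7% | 7.8 to 98.2 | 35.6 to 96.8 |
| 3 | 67.7% | −159.9 to 95.0 | −44.8 to 92.8 |

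Subtracting 1/860 + 1/185 from the variance moves the log-Wald lower limits by less than 1 point.

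**Zero active cases.** The log scale needs 1/X and fails. On p or on the untransformed relative risk, the estimated variance is zero and the interval collapses to VE = 100%. The probability is (1 − p)^5:
- VE 70%: 1.3%
- VE 90%: 0.6827^5 = 14.8%
- VE 95%: 0.8114^5 = 35.2%

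**One-sided error of log-Wald.** This is the probability, when VE is 0, that the lower limit lies above 0. It exceeds 5% at nine of the 20 counts from 5 to 24:

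| Events | 6 | 9 | 10 | 13 | 14 | 17 | 18 | 21 | 22 |
|---|---|---|---|---|---|---|---|---|---|
| Error (%) | 7.3 | 5.8 | 8.4 | 6.4 | 8.6 | 6.5 | 8.3 | 6.3 | 7.9 |

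At the other eleven counts, including 5 and 23, log-Wald has the same rejection set as the exact test, with zero active cases counted as a rejection.

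**Power at 5 events, VE 90%, by reading of Wald.**
- Log scale, X = 0 gives no interval: 0.3446 + 0.3204 = 66.5%
- Log scale, X = 0 counted as success: 81.3%
- Wald on p: 81.3%
- Untransformed relative risk: 81.4%, or 96.2% with X = 0 counted, but with one-sided error 21.6%

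**The case against.** A reader might infer that Wald fails to deliver the stated 80% power. The SAP does not support that. The 66.5% requires both the log scale and treating 0 of 5, the strongest evidence for efficacy, as a failure. Counting it as success, or applying Wald to p, gives 81.3%. At 23 events log-Wald rejects at X ≤ 15, the exact set, so that figure holds under either method. Nor are 5 and 23 arithmetic errors. What remains is that the SAP does not say which reading applies.

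The error inflation also depends on scale and count. Wald on p stays below 5% at every count from 5 to 24, and log-Wald does so at eleven of the 20. The inflation is real at the other nine, and a relative-risk scale is the natural reading because the amendment names a relative risk.

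The exact method has costs of its own: an error of only 1.1% at 6 events, much wider intervals in places, and power at VE 90% that drops to 71.2% at 6 events.

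Finally, section 7.5 lists these efficacy endpoints as exploratory, and a footnote in section 7.7.3 says no formal tests are made. Case counts are tabulated whatever the interval does, and harm monitoring in section 7.7.2 uses Newcombe limits. Zero active cases become unlikely as events accumulate (2.2% at 10 events and VE 90%). Section 1 leaves output detail to the Data Presentation Specification, which is not at hand and could hold a zero-cell rule. All this lowers the severity. It does not rescue the amendment's reason.

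**Conclusion.** The point holds at moderate severity. The stated reason for dropping Clopper-Pearson is wrong for the SAP's formula. The planned interval is undefined or has zero width with no active cases, a 14.8% outcome at the 5-event threshold in the SAP's own 90% scenario. On the log scale it overstates certainty at nine of the 20 counts from 5 to 24. The power rationale matches the exact method; whether the planned method shares it at 5 events depends on a scale and a zero-cell rule that the SAP does not state.

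The calculations condition on the total number of events, hold the ratio at 860:185, and ignore unequal follow-up, including the censoring at unblinding or unscheduled vaccination.

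**What to change.** Replace the Wald sentence in section 7.7.3 with 90% Clopper-Pearson limits pL and pU for p, reported as lower VE = 100(1 − pU/(r(1 − pU))) and upper VE = 100(1 − pL/(r(1 − pL))). Apply this to the non-S ELISA endpoint too, and correct the Amendment 1 rationale. State the 80% power for exactly 5 and exactly 23 events, not for every count of at least 5. If Wald is kept, name the scale, give a rule for zero active cases and recompute the power.

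The cost is SAP wording and a small program change. The intervals become wider and conservative: at 3 of 5 the lower limit moves from about −45% to −160%. If all events fall in the active group, the VE estimate and lower limit are unbounded and only an upper limit can be reported (73.8% at 5 of 5).

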6. POPULATIONS FOR ANALYSIS

For vaccine studies, study intervention assignment will follow the as treated principle: all analyses (including safety, immunogenicity and efficacy analyses) will be analyzed by the actually received vaccine.

Population	Description
All screened participants (ALL)	The “all screened participants” set includes all participants that were screened, regardless of whether they were enrolled and/or randomized.
All randomized participants (ALL RANDOMIZED)	The “all randomized participants” set includes all participants that were randomized to one of the treatment groups.
Full Analyses Set (FAS)	The full analysis set will include all participants with at least one vaccine administration documented.
Per Protocol Immunogenicity Set (PPI)	The per protocol immunogenicity population will include all randomized and vaccinated participants for whom immunogenicity data are available excluding participants with major protocol deviations expecting to impact the immunogenicity outcomes. In addition, samples obtained after missed vaccinations or participants with natural infection occurring after screening (if applicable) will be excluded from the analysis set.
Per Protocol Efficacy Set (PPE)	The per protocol efficacy population will include all randomized participants having received at least 1 vaccination for whom efficacy data concerning endpoint measures are available. All efficacy analyses will be done according to the as treated principle (ie, actually received vaccinations).

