- “Post-Dose 1 and Post-Booster Doses Combined”, which refers to the complete regimen including all the booster doses in Cohort 2a. It includes the 28-day period after each vaccination (dose 1, booster dose 1, and booster dose 2).
- “Post-Dose 1, Post-Dose 2 and Post-Booster Doses Combined”, which refers to the complete regimen including all the booster doses in Cohort 2b. It includes the 28-day period after each vaccination (dose 1, dose 2, booster dose 1, and booster dose 2).

For some tables, e.g. SAE tables, a period “Entire study” will be defined. This will be a combination of all the active phases and periods, so that it covers the time window from vaccination 1 up to and including the end of the study (per participant).

The primary endpoint includes SAEs from the first vaccination until 6 months after completion of the primary regimen for cohorts 2a and 2b. This will be a combined period of post-dose 1 and post-dose 1 Follow Up (FU) (for Cohort 2a) and a combination of post-dose 1, post-dose 1 FU, post-dose 2, and post-dose 2 FU (for Cohort 2b). This period will be labeled “Entire Primary Regimen” or similar in the outputs.

The exploratory endpoints include SAEs from the first booster vaccination time point until the end of the regimen for Cohort 2. This will be a combined period of post-booster 1 until the last follow-up period in Cohorts 2a and 2b. This period will be labeled “Entire Booster Regimen” or similar in the outputs.

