The number and percentage of participants with at least one positive non-S protein ELISA (e.g., N ELISA), if available, will be tabulated by vaccine regimen. The analysis will be repeated pooling all active regimens vs. placebo, where data from all cohorts will be pooled. If at least 5 positive non-S protein ELISA events have been observed, VE can be calculated against this endpoint, using the same approach as outlined above for the VE against molecularly confirmed SARS-CoV-2 infection.

For each participant with confirmed COVID-19 infection, a narrative will be prepared based on the visit performed 28 days after the onset of COVID-19 signs and symptoms and other selected information from the clinical database, as available:

- participant ID
- vaccination regimen
- sex, race, ethnicity, age, BMI, dates at which vaccinations were received
- physical examination findings based on the visit performed 28 days after the onset of COVID-19 signs and symptoms
- vital signs including body temperature based on the visit performed 28 days after the onset of COVID-19 signs and symptoms
- concomitant medications since symptom onset
- Humoral immune responses as collected at the planned time points + those obtained from the blood sample taken on the visit performed 28 days after the onset of COVID-19 signs and symptoms. This information may be presented graphically.

For the analysis of the SIC (Patient Reported Outcomes, PRO) data, the following considerations apply

- An “episode” is defined as a period in which any symptoms are reported on the SIC, starting from the first day on which symptoms were reported until the first day that the PRO was not completed because the symptoms had resolved (this will be indicated in the SDTM data, with reason for not completing the PRO = “Symptoms resolved” (or similar) or death)
- A symptom (e.g. feeling generally unwell, fatigue, physical weakness, cough, etc.) is assumed to be present on each day the associated Yes/No question is answered “Yes” or the associated severity question has a rating > 0 .

- If the PRO was not completed due to the participant being too ill or due to the participant being hospitalized, the symptom will be considered present with severity score 10. If the PRO was not completed due to any other reason, no imputations will be done.

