7.7.4. Definition of Subgroups

Selected safety and immunogenicity analyses will be conducted by the seropositivity status (positive vs. negative) of the participant. A participant will be considered seropositive if:

1. The serological test for SARS-CoV-2-specific antibodies at baseline (if available) is positive

Note: in case multiple test results are available (IgG, IgM, IgA, no isotype specified), then as soon as one of the test results is positive, the participant will be considered seropositive.

OR

2. The S ELISA immunogenicity readout on Day 1 is considered positive.

At the time of first interim analysis of a cohort, S ELISA Day 1 data for that cohort may not be available at the time of the CRF database snapshot or lock. In that case, participant serostatus will be based solely on the serological test for SARS-CoV-2-specific antibodies at baseline. As of the second interim analysis, it is expected that S ELISA Day 1 data will have become available for the participants, so that both criteria can (and will) be applied.

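### VE against non-S ELISA positivity requires no negative baseline, so antibody persisting from infection before dose 1 counts as an event

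*SAP*

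**What the plan says.** SAP section 7.7.3 states that the number and percentage of "participants with at least one positive non-S protein ELISA (e.g., N ELISA), if available, will be tabulated by vaccine regimen", and that the analysis is repeated for all active regimens pooled against placebo across cohorts. It continues: "If at least 5 positive non-S protein ELISA events have been observed, VE can be calculated against this endpoint, using the same approach as outlined" for molecularly confirmed infection. That approach is VE = 100 × (1 − p/(r(1 − p))), where p is the share of events that fall in the active group and r the ratio of active to placebo participants, with 90% Wald limits.

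Four other places bear on who and what is counted:

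- **Molecular endpoint, section 7.7.3.** Participants with "at least one molecularly confirmed SARS-CoV-2 infection will be tabulated by vaccine regimen, for the entire study period only". The influenza endpoint carries the same restriction. The non-S ELISA endpoint does not.
- **Censoring footnote, section 7.7.3.** "Note that the observation period ends at the time of unblinding or receipt of an unscheduled vaccine, whichever occurs first". It applies to all efficacy analyses and fixes the end of observation, not its start.
- **Efficacy set, section 6.** "The per protocol efficacy population will include all randomized participants having received at least 1 vaccination for whom efficacy data concerning endpoint measures are available". Prior infection is not an exclusion.
- **Serostatus, section 7.7.4.** "Selected safety and immunogenicity analyses will be conducted by the seropositivity status (positive vs. negative) of the participant". Efficacy is not among these analyses.

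**The concern.** A positive swab points to a current infection. A positive antibody result may reflect one that ended before the trial began. The vaccine cannot have prevented an infection that preceded dose 1, so a participant who brings non-S antibody into the trial says nothing about VE. Under a rule of at least one positive result, that participant is still an event.

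The SAP allows for such participants: serostatus at screening is a baseline variable (section 7.2.1), a model covariate (section 7.7.1.7) and a subgroup factor (section 7.7.4). For VNA and S-ELISA, section 7.7.1.5.1 separates a positive sample from a response relative to baseline. The non-S ELISA endpoint lacks that second step.

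At stake is an exploratory VE that could be misread as weak protection against infection, and a 5-event trigger that could be met without 5 new infections.

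**Working it through.** **1. The plan's own figure.** The 5-event rule is justified in section 7.7.3 by power for molecularly confirmed infection. With r = 860/185 = 4.65, the active share of events under VE = 0 is r/(1 + r) = 0.823. Under VE = 90% it is 0.1r/(1 + 0.1r) = 0.465/1.465 = 0.317. An exact one-sided binomial test on 5 events rejects at 2 or fewer active cases: alpha 0.042, power 81.3%. For VE = 70% the active share is 0.582; 23 events reject at 15 or fewer: alpha 0.038, power 81.2%. Both stated event counts reproduce, so the SAP's arithmetic is sound. It assumes that every event is a new infection.

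**2. Does a start at vaccination 1 remove prior positives?** Take counting to begin at the first vaccination, as the *Entire study* period of section 7.1.2 does. A pre-dose Day 1 sample then drops out. A participant who was positive on that sample and still has antibody at a later visit has at least one positive result inside the window and is counted. The window removes the sample but not the participant.

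**3. Size.** Inputs:

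- 860 active and 185 placebo participants (section 7.7.3).
- True VE of 70% or 90%, the two values used in section 7.7.3.
- q, the share non-S positive before dose 1: **assumed**, because the SAP gives none.
- a, the placebo attack rate after dose 1: **assumed**, because the SAP gives none.
- Full persistence of prior antibody to a later tested visit: **assumed**.

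Expected event proportions are q + (1 − q)a on placebo and q + (1 − q)a(1 − VE) on active. The SAP's formula reduces to one minus their ratio, so

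expected VE = true VE × (1 − q)a / [q + (1 − q)a].

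With a = 5% and true VE = 70%:

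| q | Placebo proportion | Active proportion | Ratio | Expected VE |
|---|---|---|---|---|
| 0 | 0.0500 | 0.0150 | 0.300 | 70% |
| 0.5% | 0.0548 | 0.0199 | 0.364 | 64% |
| 2% | 0.0690 | 0.0347 | 0.503 | 50% |
| 5% | 0.0975 | 0.0643 | 0.659 | 34% |

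Check through the SAP's own formula at q = 2%: active events 860 × 0.0347 = 29.8, placebo events 185 × 0.0690 = 12.8, p/(1 − p) = 29.84/12.77 = 2.34, divided by 4.65 = 0.503, so VE = 50%.

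Other assumptions, same formula:

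| True VE | a | q = 0.5% | q = 2% | q = 5% |
|---|---|---|---|---|
| 70% | 2% | 56% | 35% | 19% |
| 70% | 10% | 67% | 58% | 46% |
| 90% | 5% | 82% | 64% | 44% |

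If only half of prior positives stay positive and the rest are at risk like anyone else, q = 2% acts as 1%. With a = 5%, true VE of 70% then becomes 0.7 × 0.0495/0.0595 = 58%.

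**4. Trigger.** Prior positives alone, if all persist, give 1,045 × 0.5% = 5.2 expected events (60% chance of at least 5), or 1,045 × 1% = 10.5 (98% chance).

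**The case against.** A reader might infer that the SAP plans to count samples drawn before vaccination, so that at 2% baseline positivity some 21 of 1,045 participants (1,045 × 0.02 = 20.9) would already be events on Day 1. The document does not support that. No sentence says pre-vaccination samples count. Section 7.1.1 has efficacy results shown by phase or pooled over the entire study, section 7.1.2 starts the *Entire study* period at the first vaccination, and Table 1 ends screening one minute before the first post-dose period. The instruction to follow the molecular approach points the same way. Section 7.1.2 introduces that period for some tables, with SAE tables as its example, so this is the natural reading rather than an explicit rule. It answers the claim about Day 1 events but leaves step 2 above untouched.

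Other objections stand in part:

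- **The inputs are assumed.** At q = 0.5% and a 10% attack rate the loss is only about 3 points. Serostatus in section 7.7.4 rests on a serological test or the Day 1 S ELISA, not a non-S assay. It shows that prior infection is allowed for, not how common it is. A VE built almost wholly on infections before the trial is an extreme case.
- **The shift is an expectation.** At q = 2% the placebo group holds about 4 prior positives (185 × 0.02 = 3.7), so chance imbalance could move VE either way.
- **Little depends on it.** The assay is conditional on availability, and VE on this endpoint is permitted rather than promised. No primary or secondary endpoint uses it, and harm monitoring in section 7.7.2 uses molecularly confirmed cases.
- **Detail is deferred to the Data Presentation Specifications.** The condition could be set there. But it defines the event, and it is better fixed in the SAP before unblinded results are seen.

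**Conclusion.** The concern holds as a missing negative-baseline condition. As written, a participant infected before dose 1 whose antibody persists is an event for VE and for the 5-event trigger, and this biases VE toward zero in expectation. Under full persistence and a 5% placebo attack rate, a true VE of 70% becomes about 64%, 50% or 34% at baseline positivity of 0.5%, 2% or 5%. The direction rests on randomization and on some persistence of antibody. The size rests on three inputs the SAP does not give. Because the analysis is optional and exploratory, this is a correction worth making, not a threat to the trial's main conclusions.

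**What to change.** Define the event in section 7.7.3 as conversion: non-S ELISA negative at the last pre-vaccination sample, and at least one positive sample afterwards, before the censoring time in that section's footnote. Restrict the numerator, the denominators, r and the 5-event trigger to baseline-negative participants. List baseline positives separately by regimen. If no baseline non-S ELISA result exists, use the baseline serostatus of section 7.7.4 and say so.

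The cost is a few sentences, the loss of baseline-positive participants from this one analysis, and the need for a baseline result on each participant, which the SAP does not show to be available. The serostatus fallback relies on different tests from the endpoint assay, so some misclassification may remain.
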